At the 2nd-week re-evaluation, they will be escalated to the new dose (1mg/kg/day) if the baselines HR and BP are WNL. Patients will have HR and BP noted after first new dose (1mg/kg/day) of propranolol to ensure that the propranolol is tolerated. If the HR and BP are WNL, they will continue on this new dose and re-evaluated in 2 weeks for the 4th-week evaluation. If they have a drop in HR and BP to below normal range, they will be de-escalated and remain on the prior dose (0.5mg/kg/day) until the next visit (week 4).

At the 4th and 6th-week evaluation, their baseline vitals will be evaluated and their propranolol escalated to the next dose (if vitals are WNL) and have their HR and BP assessed after first new dose. Propranolol will stay increased or held at old dose depending on HR and BP after the first new dose as described above. If on re-evaluation in 2 weeks a patient continues to have below normal HR and blood pressure on re-challenge of the escalated dose, they will not be escalated and remain at the last tolerated dose for the remainder of the 8 week period with no further re-challenges. For patients with below normal HR and BP and needed their doses held, they will be reported as AEs.

At each study visit, patients will be asked to complete validated questionnaire to assess for tolerance to propranolol treatment, subjective changes in lymphedema symptoms, and self-reported function and activities of daily living (SF-36, LYMPH—ICF, and LYMPH—ICF—LL) (See attached documents, Appendix 2). Physical examination will include weight and BMI, vitals (HR, BP), and measurement of girth of normal and affected extremity.

MRIs and blood tests will be performed at study entry and study endpoint to assess for changes in lymphedema tissue composition[21-23] in response to propranolol.

Blood draws will be performed at study entry, at the midpoint, and study endpoint to assess for changes in circulating biomarkers in response to propranolol treatment.

Correlative biomarkers assessed will include markers of progenitor, endothelial, lymphatic, macrophage, and adipocyte cells, and expression of beta-adrenergic receptors (Table 3).

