### **5.2 Dose Escalation Schema**

#### **5.2.1 Inter-Patient Escalation**

There is no inter-patient escalation allowed on this study.

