### 8.2.2 Sampling Schedule

In patients with skin lesions on the affected extremity, skin biopsy samples will be collected at study entry and at the two-month evaluation point (Week 8).

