## 8.4 Statistical Analysis

Descriptive statistics will be used to summarize patient characteristics, toxicity data, response data and biomarker expression. Toxicity rates at each dose tested will be presented with 95% exact confidence intervals. Responses will be evaluated among patients treated at the highest tolerable dose. Continuous outcomes will be summarized using mean  $\pm$  standard deviation or median (interquartile range) for non-normal data. Comparisons between groups and response changes from baseline will be evaluated using two-sided t-tests or the non-parametric equivalent Wilcoxon Rank-Sum test (for non-normal data). Association between PIK3CA mutational status and patient response will be assessed using chi-square/Fisher exact test. All analyses will be performed using a type I error of 0.05. Biostatistics will be done using Irving Institute for Clinical and Translational Research statistical services at Columbia University Medical Center.

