## 11.2 Study Design/ Endpoints (Table 2)

11.2.1 **Study design:** Each patient will serve as his/her own control, for comparison of study questionnaires (subjective) and with changes in the clinical measurements and imaging measurements of the anatomic area affected by lymphatic malformation compared before and after treatment (objective). In our experience, children exhibiting responses to propranolol displayed these within 2 weeks of beginning propranolol treatment, with estimated reduction in the overall volume of the affected area exceeding 20%.

11.2.2 **Primary endpoints:** The primary endpoint will be the tolerability of escalating dosage of propranolol both by subjective reporting (survey instrument) as well as objective measurements of vital signs. Survey instruments include a general quality of life (QOL) and function survey (SF-36), as well as validated survey instruments for patients with lymphedema (LYMPH—ICF, LYMPH—LCF—LL)[38, 39].

11.2.3 **Secondary endpoints:** The secondary endpoints of the study will be both subjective and objective evaluation of the lymphedema after propranolol treatment, as measured by both survey instrument and objective measurements (clinical exam and radiological studies), as well as biological assays from tissues obtained from biopsies.

11.2.3.1 We will determine whether higher doses of propranolol are well tolerated in this patient population. Secondarily, we will measure determine whether higher doses correlate with improvement in lymphedema symptoms and signs, and healing or improvement of skin lesions, if present (reduced lymphatic leakage, reduced bleeding). Skin lesions will be photographed at clinical visits, and daily lymphatic fluid losses estimated by weight measurements.

Using MRI and body composition analysis, we will determine whether propranolol decreases lymphedema, alters edema water content and location (intracellular vs. interstitial), or alters adiposity of affected extremity.

We will study the biologic activity of oral propranolol against lymphedema, by examining the expression of progenitor cell markers, lymphatic endothelial cell markers, beta-adrenergic receptor expression, macrophage markers and detection of adipocyte content of biopsy specimens (see table below). Results will be compared to ultrasound and magnetic imaging data.

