#### 11.3.2 Imaging Studies

Lymphedema MRI characteristics before and after propranolol therapy will be assessed and related to clinical outcome, as applicable. Specifically, whole body MRI will be used to evaluate body composition and changes in regional adipose tissue depots in the affected limb[21-23].

Furthermore, changes in body composition (water and fat content) in response to propranolol treatment will be evaluated in this study. To evaluate water content, the standard deuterium dilution technique will be used. Fasting patients will have blood draw before drinking stable deuterium isotopes and sodium bromide and after isotope equilibration (about 3-4 hours). Total body water, extra-cellular and intracellular water content can be calculated[22, 40]. Furthermore, a quantitative magnetic resonance (QMR) system will be used to evaluate body (fat and water) content in response to propranolol treatment[21]. Quantification and analysis of results will be performed by [name].

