#### 12.4 **Response**

Patients should be re-evaluated for response by clinical examination every 2 weeks. Baseline MRI will be obtained, and an MRI repeated at 8 weeks. Response will be evaluated in this study using quality of life survey instruments, physical examination and radiologic studies (MRI at baseline and 8 weeks).

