##### 12.4.1 Definitions

Subjective Response: Patients who complete at least the questionnaires at baseline (study entry) and at the last study visit will be included for subjective evaluation.

Evaluable for Objective Response: by physical examination and radiological studies as outlined above.

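### Section 8.4 assigns the Wilcoxon rank-sum test, which needs two independent samples, to within-patient changes from baseline; the signed-rank test should be named instead

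*Combined protocol and SAP*

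**What the plan says.** Section 8.4 covers two tasks in one sentence: comparing groups, and assessing change from baseline. Both get the same tests: "response changes from baseline will be evaluated using two-sided t-tests or the non-parametric equivalent Wilcoxon Rank-Sum test (for non-normal data". The type I error is set at 0.05. Rank-sum is the only non-parametric test the documents name for continuous outcomes.

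The design is within-patient. Section 11.2.1 says "Each patient will serve as his/her own control". Table 1 gives every patient the same escalation schedule, and section 5.2.1 adds "There is no inter-patient escalation allowed on this study". The response data are repeated measurements on the same people:

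- Questionnaires (12.4.1): "Patients who complete at least the questionnaires at baseline (study entry) and at the last study visit will be included for subjective evaluation"
- MRI (12.4): "Baseline MRI will be obtained, and an MRI repeated at 8 weeks". Section 11.3.2 also says "Lymphedema MRI characteristics before and after propranolol therapy will be assessed and related to clinical outcome, as applicable"
- Blood markers (2.4): "Blood draws will be performed at study entry, at the midpoint, and study endpoint to assess for changes in circulating biomarkers"
- Biopsies (8.2.2): "In patients with skin lesions on the affected extremity, skin biopsy samples will be collected at study entry", and again at week 8.

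Sections 2.4 and 11.3.1 specify Student's t-test for the tissue markers without saying whether it is paired. The words paired and signed-rank appear nowhere in the text supplied.

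**The concern.** For comparing different patients, such as a continuous response by mutation status, rank-sum is a suitable choice. For change from baseline in one group it is not. With no control arm, removing between-patient variation by pairing is the design's main source of precision, and the named test throws it away. An analyst faced with a non-normal outcome would have to follow the plan and use an unsuitable test, or depart from it after seeing the data. With 15 to 20 patients expected (section 11.1), there is little precision to spare.

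**Working it through.** **Plan's own figure.** There is none to reproduce. Section 11.1 bases the sample size on clinical volume, and the documents give no power, SD, effect size or within-patient correlation.

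**Can the named test do the job?** Rank-sum takes two samples from different patients.

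1. Used on baseline values against follow-up values, it treats the same patients as two unrelated groups.
2. Used on the change scores of one group, it has one sample and cannot be computed.
3. Used on change scores of two different patient groups, it is valid, but that is the between-group task and does not test change from baseline.

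**Why ignoring the pairing is conservative.** Take equal SD σ, correlation ρ and n pairs. The mean difference has variance 2σ²(1−ρ)/n, while an unpaired test assumes 2σ²/n. The standardised statistic therefore has SD √(1−ρ) under no change, and a nominal 0.05 test has a true level of roughly 2Φ(−1.96/√(1−ρ)):

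- ρ = 0.3: 1.96/0.837 = 2.34, level about 0.019
- ρ = 0.5: 1.96/0.707 = 2.77, level about 0.006
- ρ = 0.7: 1.96/0.548 = 3.58, level about 0.0003

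This is a large-sample guide for means. The rank tests were simulated directly.

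**Simulation.** From the documents: n = 15 and 20, two-sided 0.05. Assumed: ρ = 0, 0.3, 0.5, 0.7; shifts of 0, 0.5, 0.8 and 1.0 SD; lognormal data, exp(0.8z) of bivariate normal pairs, with shift and correlation on the log scale. Skewed data are used because that is when section 8.4 selects rank-sum. Exact p-values, 100,000 trials per cell.

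Power, rank-sum / signed-rank:

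| n | Shift | ρ = 0.3 | ρ = 0.5 | ρ = 0.7 |
|---|---|---|---|---|
| 20 | 0.5 SD | 0.296 / 0.381 | 0.271 / 0.494 | 0.237 / 0.698 |
| 20 | 0.8 SD | 0.698 / 0.750 | 0.723 / 0.871 | 0.771 / 0.975 |
| 20 | 1.0 SD | 0.886 / 0.906 | 0.918 / 0.970 | 0.956 / 0.998 |
| 15 | 0.5 SD | 0.202 / 0.284 | 0.173 / 0.375 | 0.139 / 0.557 |
| 15 | 0.8 SD | 0.528 / 0.613 | 0.535 / 0.746 | 0.558 / 0.915 |
| 15 | 1.0 SD | 0.747 / 0.796 | 0.777 / 0.902 | 0.828 / 0.984 |

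Type I error of rank-sum at ρ = 0.3, 0.5, 0.7 is 0.0223, 0.0088, 0.0015 (n = 20) and 0.0203, 0.0080, 0.0016 (n = 15). Signed-rank stays at 0.047 to 0.049.

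**Sensitivity, n = 20.**

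- ρ = 0: type I error is 0.049 for both; power at 0.5 SD is 0.321 for rank-sum and 0.288 for signed-rank, so there is no loss.
- Less skew, exp(0.5z), at 0.5 SD: 0.293 / 0.396, 0.272 / 0.517, 0.238 / 0.727.
- More skew, exp(1.0z), at 0.5 SD: 0.298 / 0.372, 0.269 / 0.478, 0.237 / 0.680.
- Heavy tails (t with 3 df) at 0.5 SD: 0.484 / 0.589, 0.478 / 0.723, 0.497 / 0.891. At 1.0 SD: 0.978 / 0.978, 0.985 / 0.994, 0.994 / 1.000, a loss of at most 1 point.

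A re-run of the main lognormal grid with 20,000 trials per cell agreed within about 1 percentage point.

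**The case against.** The best defence is that this is a slip in naming. Section 8.4 asks for the non-parametric counterpart of the t-test; in a before-and-after design that is the signed-rank test, and the analysis is assigned to an institutional statistics service that would see this. The sentence can also be read as comparing change scores between different patients, where rank-sum is right. The consequences are limited: the plan has no success criterion, much of the analysis is descriptive, no hypothesis test is specified for primary tolerability, and no false claim of benefit would follow. The power figures come from assumed inputs and describe only one way of misapplying the test. The real number of pairs may also be below 15 to 20, since biopsies are limited to patients with skin lesions and responses to those at the highest tolerable dose.

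Most of this bears on weight, and it stands as such. It does not remove the defect. A plan that names a specific test should name the right one, and the between-patient reading leaves the within-patient comparison with no valid non-parametric test. Two further points are fair. The unlabelled t-tests in 2.4, 8.4 and 11.3.1 are ambiguous, not wrong. For outcomes measured more than twice, such as blood markers and questionnaires, naming the signed-rank test does not by itself say which two times are compared.

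**Conclusion.** The concern holds. Section 8.4 names an independent-samples test for paired data, and no other section corrects it. If the rule were applied to baseline and follow-up values with positive within-patient correlation, the true type I error would fall to about 0.02 at correlation 0.3 and 0.002 at 0.7, with a matching loss of power. Over the assumed range with 20 patients and skewed data, the loss runs from 2 to 5 points at a 1.0 SD shift to 9, 22 and 46 points at 0.5 SD for correlations 0.3, 0.5 and 0.7. The last is the extreme of the grid. Correlation, shift and distribution are all assumptions, and at zero correlation nothing is lost.

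The affected outcomes are those judged non-normal, mainly the secondary response and biomarker measures. The questionnaires and vital signs in the primary endpoint are affected only if their changes are tested this way. Toxicity rates with exact intervals, the PIK3CA chi-square or Fisher test, and comparisons between different patients are not affected. This should be fixed, but it does not threaten the trial.

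**What to change.** Replace the sentence in section 8.4 with two, for example: *Changes from baseline will be analysed on within-patient differences by the paired t-test or, if the differences are non-normal, the Wilcoxon signed-rank test. Two-sample t-tests and Wilcoxon rank-sum tests will be used only to compare different patients.*

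As a separate clarification, state in sections 2.4 and 11.3.1 that before-and-after Student's t-tests are paired. For outcomes measured at more than two visits, name the pair of times being compared.

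One limit should be known in advance: with five pairs the smallest two-sided exact signed-rank p-value is 2/2⁵ = 0.0625, so an outcome with five or fewer pairs cannot reach 0.05 and is better reported descriptively.

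The cost is a few words of text. No data, visits or patients are added, and the planned sample size is unchanged.

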### 1.2 Secondary Aims

- 1.2.1 to assess disease-specific lymphedema patients’ response to propranolol
- 1.2.1a to assess *subjective* patient-reported lymphedema-related symptoms
  - i) Validated questionnaires: LYMPH—ICF, LYMPH—ICF--LL
- 1.2.1b to assess *objective* measures
  - i) Physical examination: Weight, BMI, limb girth discrepancy
  - ii) Imaging evaluation: MRI
  - iii) Blood and tissue analysis: circulating and tissue biomarkers
  - iv) Genetic analysis: correlation of somatic mutations to propranolol response

Table 2. Primary and secondary endpoints

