# 11.0 STATISTICAL AND ETHICAL CONSIDERATIONS

## 11.1 Sample Size and Study Duration

**Sample Size:** Based on our current clinical volume, we anticipate a total enrollment of 15-20 (this is just an example to show a range) patients over a period of 24 months.

**Accrual Rate:** We anticipate that 8-10 patients per year will be accrued to the study.

**Accrual Targets:** LMs affect the general population without known differences in genders or ethnicities. Therefore, we expect accrual to reflect the makeup of the population in the region(s) surrounding our institution.

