**Table 3. Markers to be probed and assessed in blood and tissues**

Progenitor cell markers	CD133, CD45, podoplanin, CD90, NG2
Lymphatic endothelial cell markers	VEGFR-2, VEGFR-3, podoplanin, Prox1, LYVE1
Beta-adrenergic receptors	Beta-1, beta-2, beta-3 adrenergic receptors
Macrophage markers	CD68, iNOS, F4/80

The analyses we plan to perform on the specimens have been validated by our laboratory using discarded de-identified specimens[14]. Fixed frozen tissue will be prepared and 5-micron sections generated. Standard immunohistochemistry will be performed with commercially available antibodies and H&E staining performed. Results will be captured by microscopy and digital camera. Results will be quantified using ImageJ software and *Student's t-test* to determine significance, with a  $p < 0.05$  considered significant. We have already isolated similar specimens from  $> 10$  patients and have obtained consistent results using these methodologies.

We have comprehensive data on *in vitro* and *in vivo* analysis of 12 cell lines from patients with LMs. We have demonstrated consistently that LMPCs have unique characteristics by FACS analysis and gene expression profile analysis. They express mesenchymal stem cell markers CD90 and NG2, and can be differentiated into various terminal cell types including adipocytes, mural and endothelial cells. When implanted into immunocompromised mice, these LMPCs formed cystic structures that phenocopy lymphatic malformations. These features are reproducible between LMPC cell lines, and demonstrate consistent changes in gene and protein expression after treatment with propranolol.

We are expecting to recruit 20 patients into this study. Our assays are sufficiently sensitive to detect 5-10% differences in proliferation rate and gene and protein expression changes.

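### PIK3CA status is tested against a categorical response that the protocol never defines, although most response measures are continuous

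*Combined protocol and SAP*

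**What the plan says.** Section 1.2 lists as part of a secondary aim: "Genetic analysis: correlation of somatic mutations to propranolol response". Section 8.4 fixes the test: "Association between PIK3CA mutational status and patient response will be assessed using chi-square/Fisher exact test". It adds: "All analyses will be performed using a type I error of 0.05".

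On what response is, section 12.4 says: "Response will be evaluated in this study using quality of life survey instruments, physical examination and radiologic studies". Section 12.4.1, headed Definitions, says who can be evaluated, not who has responded: "Patients who complete at least the questionnaires at baseline (study entry) and at the last study visit will be included for subjective evaluation". Its entry for objective response likewise covers evaluability only.

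The sentence in 8.4 before the PIK3CA one gives the general approach: "Comparisons between groups and response changes from baseline will be evaluated using two-sided t-tests or the non-parametric equivalent Wilcoxon Rank-Sum test".

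On numbers, section 11.1 says "we anticipate a total enrollment of 15-20", and the text after Table 3 in section 11.3.1 says "We are expecting to recruit 20 patients into this study".

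**The concern.** The PIK3CA analysis cannot be run as written. Someone must first choose a measure, or a rule for combining several, and then a cut-off. The trial has a single open-label arm and many candidate measures. With nothing fixed in advance, that choice could be made once the data are known, and the result would then be hard to interpret.

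Efficiency is also at stake. Turning a change in girth, water content or questionnaire score into two classes discards information, and at 15 to 20 patients there is little to spare. The plan gives no reason why this group comparison should depart from the t-test or Wilcoxon approach stated one sentence earlier.

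**Working it through.** **1. Is a responder defined anywhere?**
- Section 12.4 lists instruments, with no threshold and no combining rule.
- Section 12.4.1 defines evaluability.
- Section 11.2.1 mentions a volume reduction above 20%, but as past experience with children, not as a criterion.
- The Abstract's 70% positive response rate rests on patients reporting improvement, again without a cut-off.

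None of these supplies a categorical response.

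**2. What type are the response measures?** From sections 1.2, 11.2.3.1, 11.3.2, 11.3.3 and Table 2:
- Continuous, or analysed as such: weight, BMI, limb girth discrepancy, MRI and QMR fat and water, deuterium/NaBr body water, questionnaire scores.
- Ordinal or categorical as worded: CTCAE lymphedema grade, clothing size change, healing or improvement of skin lesions.

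**3. What does dichotomising cost?** The plan has no power figure for this analysis to reproduce.

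Inputs from the documents: n = 20 (section 11.3.1; upper end of 15 to 20 in section 11.1) and a 0.05 level (section 8.4).

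Inputs assumed: two-sided testing for the categorical tests (8.4 says two-sided only for the t-tests), normal outcome with equal SD, true difference d of 1.0 or 1.5 SD, mutation split 10/10 or 6/14, and a cut midway between the two group means.

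- t-test: noncentral t with 18 df, critical value 2.101, noncentrality d × √(n1·n2/(n1+n2)). For 10/10 and d = 1.0 this is 1.0 × √(100/20) = 2.236, which gives power 0.562.
- Categorical tests: the midpoint cut makes the response probabilities Φ(d/2) and 1 − Φ(d/2). These are 0.691 and 0.309 at d = 1.0, and 0.773 and 0.227 at d = 1.5. Power is the summed binomial probability of every 2×2 table with p ≤ 0.05.
- Relative loss = 1 − (categorical power ÷ t-test power).

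| Split | d (SD) | t-test | Fisher | Chi-square, uncorrected | Loss, Fisher | Loss, chi-square |
|---|---|---|---|---|---|---|
| 10/10 | 1.0 | 0.562 | 0.219 | 0.386 | 61% | 31% |
| 10/10 | 1.5 | 0.887 | 0.520 | 0.711 | 41% | 20% |
| 6/14 | 1.0 | 0.492 | 0.309 | 0.324 | 37% | 34% |
| 6/14 | 1.5 | 0.828 | 0.613 | 0.629 | 26% | 24% |

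For example, 1 − 0.219/0.562 = 0.61 and 1 − 0.613/0.828 = 0.26.

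The gain does not depend on choosing the t-test. Simulated exact rank-sum power was 52% and 86% at 10/10 (1.0 and 1.5 SD) and 76% at 6/14 (1.5 SD), each above Fisher in the same setting.

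**4. How much of the loss comes from Fisher itself?** With no true difference and half the patients responding at 10/10, Fisher's actual type I error is 0.013 and uncorrected chi-square's is 0.042. Part of the Fisher loss at 10/10 is therefore conservatism, not the cut.

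**5. Lower n.** With 15 patients split 5/10 and d = 1.5, t-test power is 0.717 and Fisher 0.402, a loss of 44%.

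**6. Other cut-points.** With a fixed cut giving 30% to 70% responders overall, n = 20, splits from 10/10 to 4/16 and d from 0.8 to 1.5, the loss runs from 29% to 99% for Fisher and from about 11% to 89% for chi-square. At d = 2.0 the Fisher loss can be as low as 15%.

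**The case against.** The strongest reply is that this is one exploratory sub-item of a secondary aim with no claimed power, that 8.4 already provides t-test and Wilcoxon for group comparisons, and that the real gap is only an undefined response. Much of this stands: no planned power is lost, and defining response is the essential step. But 8.4 names a different test for this comparison, so the continuous analysis is not what the plan commits to.

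A reader might infer several stronger points that the documents do not support:
- **Every response measure is continuous.** Not so. Grade, clothing size and lesion healing are ordinal or categorical, and a categorical test suits them.
- **The loss is a fixed fraction, such as a third to more than half.** It depends on mutation share, effect size and cut-point, none of which is given. It is 26% for Fisher at 6/14 and 1.5 SD, and chi-square, also named in 8.4, can lose only 20%.
- **Chi-square is invalid because expected counts are below 5.** This depends on unknown margins. At 10/10 with half responding, every expected count is exactly 5 (10 × 10 ÷ 20). Naming Fisher alongside may already be meant to cover small counts.
- **With very few genotyped patients, Fisher could never reject.** At 3/3 its smallest two-sided p is 0.10, but the exact rank-sum test has the same floor. At 2/4 the rank-sum floor is worse (0.133 against 0.067). This is no argument for changing the test, and the documents do not say that so few will be genotyped. Section 8.2.2 limits biopsies to patients with skin lesions, section 2.4 does not, and section 11.3.4 sequences blood as well as tissue.
- **The cut-off will be chosen after seeing the data.** The documents are silent on timing. They leave it possible, no more.

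**Conclusion.** The concern holds in limited form. Section 8.4 commits a stated secondary aim to a test that needs a categorical response, none is defined, and most of the available measures suit the continuous comparison already planned in the same section.

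At n = 20, under the normal model with a midpoint cut, differences of 1.0 to 1.5 SD and 10/10 or 6/14 splits, dichotomising gives up about 26% to 61% of t-test power with Fisher and about 20% to 34% with uncorrected chi-square. These ranges illustrate the cost under assumed inputs and are not properties of the trial. No figure in the documents is wrong. The change should be made, but it does not touch the primary endpoints.

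**What to change.** In section 8.4, replace the PIK3CA sentence with wording that:

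1. names in advance the continuous response measure or measures for this analysis, for example change from baseline in extracellular water and in limb girth discrepancy;
2. compares that change between mutation groups with the t-test or Wilcoxon rank-sum test already in the section, or with ANCOVA adjusting for baseline;
3. reports the difference between groups with a 95% CI, which will be more informative than a p-value at this sample size;
4. keeps Fisher's exact test for responses that are truly categorical, with the categories or threshold fixed before analysis. A responder table derived from continuous measures should be descriptive only.

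Section 12.4.1 should carry the matching definition, so that response means the same thing in both places. The cost is protocol and SAP wording only: no extra patients, visits, samples or measurements.
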